Does phacoemulsification and viscocanalostomy with ologen implant have a better outcome, in patients with both cataract and primary open angle glaucoma, regarding postoperative IOP control and low complications rate, compared to phacoemulsification and viscocanalostomy alone?

Hypothesis

Our hypothesis is that using Ologen implant as a spacer in the subscleral reservoir in phacoviscocanalostomy reduces fibrosis and increase the success rate of this operation.

Aim of the Work

The Aim of this study is to evaluate the use of Ologen implant as an adjuvant in phacoviscocanalostomy in patients with coexisting cataract and glaucoma.

Objectives

- To estimate the number of patients with postoperative IOP ≤ 21 mmHg after phacoviscocanalostomy with ologen implant compared to phaco-viscocanalostomy alone 2 years after surgery.
- 2. To measure complete and qualified success rates after phaco-viscocanalostomy with ologen implant compared to phaco-viscocanalostomy alone 2 years after surgery.
- To report and describe early and late postoperative complications after phacoviscocanalostomy with ologen implant compared to phaco-viscocanalostomy alone 2 years after surgery.

Subjects and Methods

Before initiating this study, the protocol, the informed consent form and any other written information to be given to patients was reviewed and approved by the Ethics Committee of the Alpha vision center.

The investigator will explain to each patient the nature of the study, its purpose, the procedures involved, the expected duration, the potential risks, benefits involved, and any discomfort may be caused.

Each patient will be informed that participation is voluntary, that he or she may withdraw from the study at any time and without giving reasons. The withdrawal will not affect the subsequent medical or conservative treatment or relationship with the treating surgeon.

Technical Design

Center: Alpha vision center

Design: A prospective randomized controlled clinical trial.

Subjects: Patients will be collected from the outpatient clinic of Alpha vision center. The patient will be randomly assigned using simple randomization method to receive either Phacoemulsification and viscocanalostomy or Phacoemulsification and viscocanalostomy with Ologen implant.

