Study sample: Based on previous studies by Shaarawy and Mermoud ^[5], the mean IOP at the first postoperative day was 6.4 (SD=3)mmHg for the DS-treated eyes, and 3.7 (SD=2)mmHg for the DSCI-treated eyes, the minimum total sample size of 32 will be sufficient to detect a power of 80% and a significance level of 5%. To allow for 25% losses, the sample was further increased to 81. Sample size estimation was performed by G power statistical package.

Inclusion criterion:

The inclusion criteria are the presence of significant cataract interfering with vision (visual acuity ≤ 0.5) in the presence POAG. Patients are included if cataract is associated with uncontrolled glaucoma, (IOP > 21 mmHg despite maximally tolerated medical therapy) or if the IOP is ≤ 21 mmHg with use of at least two antiglaucoma drugs with medication intolerance, poor patient compliance, patients cannot attend medical supervision or have visual field deterioration.

Exclusion criteria:

Patients will be excluded if they have closed-angle glaucoma, other types of open angle glaucoma (OAG), e.g. pigmentary glaucoma, inflammatory glaucoma or neovascular glaucoma, previous ocular trauma or surgery, lens subluxation or other eye diseases affecting the vision, e.g. anterior uveitis. Patients were also excluded if there is a large perforation of the Descemet's membrane with iris prolapse during surgery (cases with microperforation, which is defined as small perforation with no associated iris prolapse, occurring

during surgery will not be excluded) or if they have other intraoperative complications that might affect the IOP, e.g. vitreous loss.

Operational Design:

Patient histories will be taken including age, gender, previous ocular surgery, trauma or any previous ocular inflammation, e.g. keratitis, iridocyclitis, etc. Slit-lamp examination will be done for examination of anterior chamber angle, determination of the type of glaucoma and the degree of cataract, measuring IOP (using Goldmann applanation tonometer), assessment of optic nerve head and retinal examination, if possible. Visual acuity (VA) was expressed in decimal fraction.

Surgical procedures:

All operations will be carried out by one surgeon using peribulbar anesthesia.

After phacoemulsification, a traction suture in the cornea is made using 8-0 polyglactin 910 (Vicryl[®], Ethicon Inc, Bridgewater, NJ, USA).

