A fornix based conjunctival flap is fashioned and no cautery is applied. Hemostasis is only achieved by using a microsponge soaked with 1/100,000 adrenaline. A superficial scleral flap of 5 x 5 mm is made and dissection is done 2 mm into the clear cornea. A smaller deeper flap of 4 x 4 mm is made until deroofing of Schlemm's canal is achieved. Decompression of the eye is done through one of the paracentesis incisions, then blunt dissection with a microsponge is done to create a descematic window that extended over Descemet's membrane until 1 to 2 mm inside the clear cornea. Subsequently, the sides of the deep flap is freed from the adjacent sclera by Vannas scissors and the deep flap is cut by the same scissors.

The juxtacanalicular trabeculum is removed and then the two openings of Schlemm's canal are cannulated on both sides using a viscocanalostomy cannula (Eagle labs, Rancho Cucamonga, CA, USA) and high-viscosity sodium hyaluronate (Healon GV; Abbott Medical Optic Inc., Santa Ana, CA, USA) is injected into the canal on both sides.

In the Phacovisco group, the superficial flap is closely sutured using four interrupted 10-0 nylon sutures, and then Healon GV is injected into the subscleral lake.

In the OloPhacovisco group, a 4 x 4 mm piece of Ologen[®] (Model: 862051 "12mm(D) x 1mm (H)") (Aeon Astron Europe B.V., Leiden, The Netherlands) is fashioned to be nearly of the same size as the cut deep scleral flap to fit inside the subscleral reservoir (Fig 2). Then the superficial flap is sutured tightly over it using four interrupted 10-0 nylon sutures (Ethilon[®], Ethicon Inc, Bridgewater, NJ, USA). Some air is injected from the paracentesis inside the eye. Then conjunctiva is closed using 8-0 polyglactin 910 sutures (Vicryl[®], Ethicon Inc, Bridgewater, NJ, USA).

Postoperative management included topical administration of 0.5% moxifloxacin drops with a tapered schedule of 1% prednisolone acetate. Antiglaucoma medication is ceased after surgery in all cases.

Follow-up:

Postoperatively, follow-up examination will be done on days 1, 7, 14 and 30, then every 2 months for 2 years. The follow-up examination includes assessment of IOP, VA and slit-lamp examination. Postoperative complications will be recorded. Signs of inflammation, such as cell infiltration and flare, is recorded and graded from 0 to 4.

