Nd:YAG laser goniopuncture is considered in all cases with elevated postoperative IOP above 21 mmHg after discontinuation of corticosteroid eye drops for at least 14 days. The Nd:YAG goniopuncture is performed using an Ellex Super Q YAG laser machine (Ellex Medical Lasers Ltd., Mawson Lakes, SA, Australia) and the gonioscopy mirror of Goldman three mirror universal laser lens (Ocular, Bellevue, Washington, USA) with a laser power setting of about 3 to 6 mJ and using about 2 to 15 shots aiming at the opening of the trabeculo-Descement window, the number of laser shots needed to open the Descemet's membrane was counted and recorded in each group. Antiglaucoma drugs will be prescribed if the IOP is elevated above 21 mmHg after considering Nd:YAG laser goniopuncture.

The main outcome measures are the IOP at the 2-year follow-up and the overall success, which included complete success when IOP is \leq 21 mmHg without any antiglaucoma drugs, and qualified success if IOP is \leq 21 mmHg with the use of a single antiglaucoma medication. Failure is considered if IOP \leq 21 mmHg cannot be reached even with the use of a single antiglaucoma medication and after performing Nd:YAG laser goniopuncture, at any follow-up visit. The secondary outcome measures were surgical complications, the use and results of Nd:YAG laser goniopuncture and visual acuity results. The last data for failed cases were used for further statistical analysis.

RESULTS

Collected data will be presented in Tables and analyzed by computer software using appropriate statistical methods.

DISCUSSION

Discussion will be done on results compared to relevant literatures and scientific researches to explain the reasons for getting such results.

Conclusion and Recommendations

Conclusion and Recommendations will be derived from the findings of the study.

Statistical analysis plan:

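### If patients are allocated before surgery, excluding them for intraoperative complications is a post-randomisation exclusion, and the plan does not provide for analysing or reporting them by arm

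*Combined protocol and SAP*

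**What the plan says.** Under Technical Design, patients come from the outpatient clinic, and "The patient will be randomly assigned using simple randomization method to receive either" phacoemulsification with viscocanalostomy alone or the same operation with Ologen. No time of allocation relative to surgery is given.

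Under Exclusion criteria there are two grounds that can be known only in theatre. The first reads "Patients were also excluded if there is a large perforation of the" Descemet's membrane, with iris prolapse. The second applies "if they have other intraoperative complications that might affect the IOP, e.g. vitreous loss". Small perforations stay in: "cases with microperforation, which is defined as small perforation with no associated iris prolapse" are expressly not excluded.

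Under Surgical procedures, "All operations will be carried out by one surgeon using peribulbar anesthesia". The description is the same for both arms up to the point where the two openings of Schlemm's canal "are cannulated on both sides using a viscocanalostomy cannula" and viscoelastic is injected. The arms separate at closure, beginning with "In the Phacovisco group, the superficial flap is closely sutured using four interrupted 10-0 nylon sutures".

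The outcome paragraph under Follow-up makes IOP at 2 years and IOP-based success the main outcomes, and adds "The secondary outcome measures were surgical complications" together with goniopuncture and visual acuity. Its one data-handling rule keeps the last data of failed cases. The Statistical analysis plan lists tests and a significance level and names no analysis population.

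**The concern.** Randomisation makes the arms comparable only if the patients compared are those who were randomised. On the natural reading of Technical Design, the arm is fixed before the operation, so removing patients for what happens during it breaks that comparison.

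Three features make this more than a formality:

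- The residual criterion is a judgement about whether a complication might affect IOP, and IOP is the main outcome.
- One surgeon operates on everyone, and nothing says that the allocation is concealed from that surgeon until the arms diverge. The criterion could therefore be applied differently by arm.
- Nothing says that excluded patients are followed, analysed, or counted by arm with reasons, so a reader of the results could not check.

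The stakes are the between-arm difference in IOP and success, the absolute success rates in each arm, and the count of surgical complications. The last would omit large perforations and vitreous loss while keeping microperforations.

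**Working it through.** **Step 1. The plan's own figure.** The concern rests on no stated number. For completeness, the minimum total of 32 under Study sample does reproduce. The difference is 6.4 - 3.7 = 2.7 mmHg, the SD is sqrt((3² + 2²)/2) = 2.55, and d = 1.06. A two-sided t test at 5% then needs 16 per arm, with power 82.6%. With 25% of 81 lost, about 60 remain, and power for that planning difference is about 98%. The issue is therefore bias, not power.

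**Step 2. Does timing matter?** Set Technical Design against Surgical procedures:

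- If allocation is before surgery, every intraoperative exclusion is post-randomisation.
- If allocation is at closure, most of the named events come first and are ordinary eligibility exclusions.
- The documents support the first reading (clinic patients assigned to whole operations) but do not state it.

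**Step 3. Sensitivity of the success difference.** The documents give no complication rate, so all inputs here are assumed except the total of 81. As randomised, success is 28/40 = 70.0% in control and 29/41 = 70.7% with Ologen, a difference of +0.7 points. Let kC and kO eyes be excluded, and let excluded eyes succeed with probability p:

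- control = (28 - kC·p)/(40 - kC)
- Ologen = (29 - kO·p)/(41 - kO)

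| Excluded (control/Ologen) | p = 0 | p = 0.35 | p = 0.70 |
|---|---|---|---|
| 2/6 | 73.7% v 82.9% (+9.2) | 71.8% v 76.9% (+5.0) | 70.0% v 70.9% (+0.9) |
| 5/1 | 80.0% v 72.5% (-7.5) | 75.0% v 71.6% (-3.4) | 70.0% v 70.8% (+0.8) |
| 3/3 | 75.7% v 76.3% (+0.6) | 72.8% v 73.6% (+0.7) | 70.0% v 70.8% (+0.8) |

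For example, at 2/6 and p = 0: 28/38 = 73.7% and 29/35 = 82.9%.

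The difference moves only when exclusions are uneven and excluded eyes do worse. With even exclusion it barely changes, but both success rates rise, to about 76% at p = 0.

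**Step 4. How unusual are the uneven splits?** If exclusion is unrelated to arm, take a binomial with probability 0.5, two-sided:

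- 8 exclusions at least as uneven as 2/6: 2 × (1 + 8 + 28)/256 = 74/256 = 0.29
- 6 exclusions at least as uneven as 5/1: 2 × (1 + 6)/64 = 14/64 = 0.22

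Such splits can easily arise by chance. The table shows sensitivity, not demonstrated bias.

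**Step 5. The complication outcome.** If 2 to 8 of 81 patients (2.5% to 9.9%, assumed) have an excluding event and are dropped, the analysed set shows 0 of 79 to 0 of 73 such events.

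**The case against.** The best case for the plan has four parts.

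- **Timing.** The time of allocation is unstated, and recruitment from a clinic says where patients come from, not when they are randomised. If allocation is at closure, most of these events are eligibility exclusions, which fits their place in the document. This stands as a condition on the finding. It is also the reason the plan must state the time.
- **Shared steps.** The named events arise mostly before the arms differ, so the implant is unlikely to cause them. Large perforation is tied to iris prolapse, and microperforation is defined and kept, which narrows discretion. This too stands, and the bias may well be small. It does not deal with the open-ended criterion, chance imbalance, or a surgeon who knows the arm.
- **Complications.** The plan never says that excluded patients leave the complication count. That is true, but excluding a patient from the study ordinarily does so, whatever the time of allocation, and nothing provides otherwise. The complications objective covers postoperative events, so it is affected less than the secondary outcome.
- **Loss allowance.** The 25% may be meant to cover these patients. The plan does not say so, and an allowance for losses protects numbers, not comparability.

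The magnitudes are also assumed. The largest needs 6 of 41 Ologen eyes (15%) excluded against 2 of 40 (5%), all of them failures, and IOP at 2 years is not illustrated.

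**Conclusion.** The concern holds, conditional on allocation before surgery, which is the natural but unstated reading. Under it, the plan excludes randomised patients on a partly discretionary criterion linked to the main outcome and gives no rule for analysing or reporting them by arm.

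The size and direction of any bias in the between-arm difference cannot be determined from the documents. In the assumed scenarios the difference ranges from -7.5 to +9.2 points against a true +0.7, and hardly moves when exclusions are even or when excluded eyes do as well as the rest. Absolute success rates are overstated only if excluded eyes do worse than retained ones. Rates of intraoperative complications are understated under either timing, unless excluded patients are counted separately.

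This should be fixed before the trial proceeds. It is not a fatal flaw.

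**What to change.** 1. **State when the allocation is revealed.** The preferred point is in theatre, after both openings of Schlemm's canal have been cannulated and before the superficial flap is closed, because the described surgery is identical up to there. Keep the allocation from the surgeon until then. Count and describe patients excluded before allocation.
2. **Drop the exclusion for anything that happens after allocation.** Follow and analyse every randomised patient in the assigned arm. Prespecify how patients who cannot be classified are handled, for example as failures for the success outcome, with a separate rule for IOP at 2 years. Use the set without patients who had such complications only as a sensitivity analysis.
3. **Report intraoperative complications for everyone operated on**, including those excluded before allocation, and by arm for those allocated.

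If allocation has to stay preoperative, items 2 and 3 still apply and protect the comparison.

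The cost is a few protocol sentences and a later opening of the allocation. Reported success may be slightly lower. If 81 randomised is kept as the target, more operations are needed: 81/0.98, 81/0.95 or 81/0.90, that is 83, 86 or 90, if 2%, 5% or 10% (assumed rates) are excluded before allocation.

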Combined phacoemulsification and viscocanalostomy with Ologen implant versus combined phacoemulsification and viscocanalostomy

Document Date: 1/5/2013

Introduction

Surgical treatment of glaucoma is indicated in cases of failure of medical treatment. Trabeculectomy is considered the standard surgical treatment of glaucoma. Nonpenetrating glaucoma surgeries, e.g. viscocanalostomy and deep sclerectomy, are becoming good alternatives. Viscocanalostomy has fewer complications than trabeculectomy, e.g. bleb leak, hypotony and bleb-related infections. ^[1–4]

Since the prevalence of both cataract and glaucoma increases with age, phakic patients who are scheduled for glaucoma surgery may also require cataract extraction, or patients scheduled for cataract surgery may be scheduled for combined surgery. Improvement of phacoemulsification techniques and stable anterior chamber depth with non-penetrating glaucoma procedures may favor combined viscocanalostomy and cataract surgery in patients with glaucoma and a coexisting cataract.^[4]

A biodegradable porous collagen-glycosaminoglycan copolymer matrix implant (Ologen[®]) is a simple chemical analog of extracellular matrices and has been used as an adjuvant to increase the long-term success of trabeculectomy. The degradation time of this type of implant is around 180 days; this implant consists of porcine based, lyophilized, crosslinked type I atelocollagen (\geq 90%) and glycosaminoglycans (\leq 10%). During trabeculectomy surgery it is placed subconjunctivally and acts as a spacer to mechanically separate the subconjunctival and episcleral tissues to decrease subconjunctival fibrosis.^[1,3]

Rationale

Primary open angle glaucoma is the second leading cause of blindness worldwide which needs effective attention otherwise it will lead to progressive optic nerve damage and eventual blindness.

The current surgical treatment of choice for medically uncontrolled glaucoma in association with cataract is combined phaco-trabeculectomy. However, this procedure is associated with both early and late postoperative complications.

Combined Non-penetrating glaucoma surgeries with phacoemulsification have been developed offering both surgeon and patient a safer, more convenient option.

With the use of Collagen implant with phaco-viscocanalostomy, it is expected to improve the pressure lowering effect of this procedure and increasing the success rate.

Research Question

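### Success is defined by an upper IOP limit only, so an eye with hypotony at 2 years counts as a success

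*Combined protocol and SAP*

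**What the plan says.** The Follow-up section sets two main outcomes, the 2-year IOP and "the overall success, which included complete success when IOP is" no higher than 21 mmHg with no antiglaucoma drug. Qualified success uses the same ceiling with one drug. Failure means that the ceiling "cannot be reached even with the use of a single antiglaucoma medication and after performing Nd:YAG laser goniopuncture, at any follow-up visit".

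The first objective has the same one-sided form: "To estimate the number of patients with postoperative IOP ≤ 21 mmHg after phacoviscocanalostomy with ologen implant", "compared to phaco-viscocanalostomy alone 2 years after surgery". The second objective measures complete and qualified success at the same time point.

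Hypotony is mentioned once, in the Introduction: "Viscocanalostomy has fewer complications than trabeculectomy, e.g. bleb leak, hypotony and bleb-related infections". It has no threshold there, and it is not named among the outcomes. Surgical complications are a secondary outcome, and the third objective reports early and late complications.

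**The concern.** The Research Question asks whether the implant gives better IOP control together with a low complication rate. The success rule has a ceiling but no floor, so it can record a complication that the protocol itself names as control achieved. This is a stated rule that can give a wrong result when followed exactly; it is more than missing detail.

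The Rationale expects the implant to strengthen the pressure-lowering effect. If that produced more late hypotony in one arm, the wrongly credited eyes would not be balanced, and the comparison of success rates would be affected as well as the rates themselves. The other main outcome gives no protection: 2-year IOP is compared as a mean, and a hypotonous eye pulls the mean down.

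**Working it through.** **1. Classify one eye under the rules as written.** Take an eye on no drugs at 2 years with an IOP of 3 mmHg (an assumed value, for illustration).

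- Complete success: 3 ≤ 21 and no drugs, so yes.
- First objective: 3 ≤ 21, so it is counted.
- Failure: the ceiling has been reached, so no.
- Complications: the eye may be recorded there, but no rule links that record to success status.

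The same eye on one drug would be a qualified success. Low IOP is never a failure at any visit.

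**2. Reproduce the planning figure.** The Study sample paragraph gives day-1 IOP of 6.4 mmHg (SD 3) after deep sclerectomy "and 3.7 (SD=2)mmHg for the DSCI-treated eyes", with 80% power, 5% significance and a minimum total of 32.

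- Common SD = √((3² + 2²)/2) = 2.55
- d = (6.4 − 3.7)/2.55 = 1.059
- A two-sided t-test with equal arms needs 15.02 per arm, rounded up to 16, so 32 in total (power 82.6%).

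The stated 32 is reproduced, so these day-1 values are the planning inputs.

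**3. What those inputs imply about day 1.** The documents give no hypotony threshold, so 3 to 6 mmHg is an assumed range. Under a normal approximation, the share below 5 mmHg is Φ((5 − 6.4)/3) = 32% without the implant and Φ((5 − 3.7)/2) = 74% with it. The ranges below cover normal, lognormal and gamma distributions with the same means and SDs.

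| Assumed threshold | No implant | Collagen implant |
|---|---|---|
| < 3 mmHg | 7–13% | 36–44% |
| < 4 mmHg | 20–22% | 56–66% |
| < 5 mmHg | 32–37% | 74–80% |
| < 6 mmHg | 45–53% | 87–89% |

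The direction is the same in every row. These shares are inferred from means and SDs; the documents report no frequency of low IOP. On the same normal approximation, the chance of exceeding 21 mmHg without the implant is about 6 × 10⁻⁷, so a ceiling alone would exclude almost none of these eyes.

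**4. What can be said at 2 years.** If h of n eyes in an arm are hypotonous and otherwise meet the rule, that arm's success rate is overstated by h/n. The between-arm difference is distorted by h₁/n₁ − h₂/n₂, which is zero if the two shares are equal. The documents give neither h, so neither the size nor the sign can be computed.

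Only the weight of a single eye is available. If the 81 patients split about equally (an assumption; the ratio is not stated), there are about 40 per arm, and one eye is 1/40 = 2.5 percentage points. After the allowed 25% losses, 81 × 0.75 = 60.75, or about 30 per arm, and one eye is 1/30 = 3.3 points. This is a scale, not an estimate of how many eyes would be affected.

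**The case against.** The strongest reply is that the day-1 figures have little to do with the success outcome. They come from deep sclerectomy with and without a collagen implant in fellow eyes, not from phacoviscocanalostomy with Ologen. They describe the first postoperative day, while success is judged at 2 years, and the Introduction puts degradation of the implant at around 180 days. Transient early low IOP would not affect 2-year success even with a floor in place. All of this stands. A reader might infer from 6.4 v 3.7 mmHg that the planning data show more hypotony with the implant in this trial. They show only that early low IOP may differ between arms.

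A reader might also infer that any error must favour Ologen. The documents do not support that. A lower mean is expected with the implant, but nothing reports more 2-year hypotony in that arm. The success rule is also categorical: without drugs, 3 and 20 mmHg score the same, so lower pressure earns no extra credit.

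Finally, complications are recorded at follow-up and compared as a secondary outcome, and visual acuity is reported, so late hypotony would probably not be hidden altogether. That is fair. It does not correct the success count, though, and with no definition of hypotony the complication count itself rests on judgement.

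**Conclusion.** The defect is in the text and does not depend on the planning data. Complete success, qualified success and the first objective have an upper limit only, so an eye with hypotony at 2 years counts as a success.

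The effect on the result is unknown. It is nil if no eye is hypotonous at 2 years. Otherwise each such eye carries about 2.5 to 3.3 percentage points of its arm's success rate, assuming arms of about equal size. Misclassification could differ by arm, because the implant is expected to lower IOP more, but the documents establish neither its size nor its direction. The conclusion is that the outcome definition should be repaired, not that the success rate is shown to be inflated in the implant arm.

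**What to change.** Before data are examined, the sponsor should:

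- write one definition of hypotony, since none exists in the documents, with the threshold or criteria left to the sponsor;
- use it for the complication record and as the lower limit for complete success, qualified success and the first objective at the 2-year visit;
- report the number of hypotonous eyes by arm, and success by arm with and without the lower limit;
- if the limit is numeric, repeat the success analysis at two values as a sensitivity analysis.

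Early transient low IOP stays a complication only and does not change success status. The count of hypotonous eyes by arm will also help readers to interpret the comparison of mean IOP.

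The cost is a definition, matching edits to the outcome paragraph and the first objective, and a few extra rows in the results. IOP is already measured at every follow-up visit. The downside is that the success rate may fall slightly.
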